Education of Municipality-based Physiotherapists in Managing Chronic Low Back Pain - an Observational Study

Date

March 20th 2023

Ethical committee reference number

S-20222000 - 156

Objective

To investigate potential changes in patient outcomes following an educational intervention aimed at upskilling physiotherapists in individualized bio-psycho-social management of patients with disabling low back pain (dLBP) in municipality rehabilitation settings. Focus will both be on changes in patient reported outcomes as well as changes in clinician behavior. Likewise, the feasibility of implementing such changes within municipality settings will be evaluated

Method

Design

A prospective, observational case-control study

Participants

Patients with dLBP referred to municipality-based rehabilitation from the Spine Centre of Southern Denmark. Eligibility is determined on the following criteria:

Inclusion Criteria:

- Referred to municipality rehabilitation from the Spine Centre of Southern Denmark
- Over 18-65 years
- Speaks and comprehends Danish
- A score over 40 on the Örebro Musculoskeletal Pain Questionnaire
- Low back pain as dominating cause for referral
- Can receive digital mail in E-boks (electronic communication platform)

Exclusion Criteria:

- A current diagnosis of psychiatric illness that precludes participation in rehabilitation
- a neurologic disorder or other disease that may affect the ability to participate in a municipality-based rehabilitation program
- neurological deficits related with radiographically confirmed lumbar spinal stenosis or radicular pain correlating with the clinical presentation
- Recent (within 6 months) history of a stabilizing operation of the low back

Procedures

Data collection:

All demographic information will be collected at baseline. This includes age, gender, weight, smoking (yes/no), diagnosis, duration of symptoms, job status (Working Yes/No. If Yes: normal capacity or reduced capacity because of back pain. If No: Full-time sick-listed because of back pain or sick-listed due to other reasons) if early retirement: due to back pain?), highest completed education beyond elementary school)

Primary Outcome

Roland Morris Disability Questionnaire 3 months after entering the study

Secondary outcomes

- Pain intensity (lower back and leg) 3 months after entering the study with a numeric rating scale (NRS:0-10)
- Örebro Musculoskeletal Pain Questionnaire 3 months after entering the study
- Self-perceived ability to work (NRS: 0-10) 3 months after entering the study
- Patient satisfaction, 7-point Likert scale 3 months after entering the study

Other Pre-specified Outcome Measures:

- Checklist to determine the competency of clinicians immediately after study completion
- Barriers and facilitators for implementing new knowledge in clinical practice – qualitative interview

3 month follow-up

- Roland Morris Disability Questionnaire at 3 months after discharge
- Pain intensity (lower back and leg) with a numeric rating scale (NRS:0-10)
- Self-perceived ability to work (NRS: 0-10)
- Patient Assessment of Transitions in Healthcare (PATH)
- Patient satisfaction, 7-point Likert scale

Other Pre-specified Outcome Measures:

- Checklist to determine the competency of clinicians and to assess interrater reliability between clinical supervisors
- Barriers and facilitators for implementing new knowledge in clinical practice – qualitative interview

Schedule of procedures and assessments (for a schematic overview, see fig. 1)

1. All participating physiotherapists (N=25) will recruit eligible patients (N=4 each, total N=100) who are asked to fill out project-specific questionnaires (see *procedures*) at the start and at the end of the rehabilitation program.
2. The participating physiotherapists will undergo a 13-day educational intervention (see description below under *intervention*) focusing on management of low back pain within an individualized multidimensional framework.
3. Point 1 is repeated on an additional 100 patients who undergo rehabilitation after the physiotherapists have completed the course
4. Participating physiotherapists will be evaluated on the background of a competency checklist which is scored by clinical supervisors connected to the study. The checklist will be scored after watching a video recording of a patient consultation performed by the physiotherapist in focus. The checklist covers 6 domains: Subjective and objective assessment, cognitive-functional therapy intervention, style of communication, patient's unhelpful pain behavior, and an overall assessment
5. Physiotherapists who demonstrate high and low competency (as determined by the evaluation of competency, point 4) are invited to participate in a semi-structured interview. The interview will explore the physiotherapists' experience of changes in management (if

any) after the educational intervention. This includes challenges, barriers and facilitating factors.

Intervention

All procedures will be based on the physiotherapists assessment where individual needs and goals are embedded into the rehabilitation. The project will investigate whether priorities within assessment and choice of management change after the educational intervention. The educational program for the physiotherapists will run over 13 days and is divided into 3 overlapping modules.

Module 1 (5 days) – Evidence-based theory

The module will focus on theoretical and practical aspects of the management of patients with back pain within a multidimensional framework. This includes differential diagnostics, social medicine measures, communication training with a focus on motivational interview and management of patients with dominant cognitive and emotional factors.

An evidence-based overview of contributing factors to the pain experience will be addressed including lifestyle, emotions, cognitions, response to pain including protective movement strategies, co-morbidity, activity level, physical/mental stress, patho-anatomy, nervous system sensitivity and social factors.

[figure not shown]
Module 2 (3 days) – Masterclass

Masterclass in where two experienced clinicians from the project group will demonstrate patient examinations and management of complex low back patients. The purpose is to help the participants gain insight into clinical application of relevant multi-dimensional management of dLBP. These demonstrations provide the platform for the following module 3.

Module 3 (5 days) – Clinical supervision

In the supervision sessions the participants receive training/guidance in integrating the theoretical and practical skills from the previous modules. Feedback/evaluation from supervisors ensures that the participants adapt a multi-dimensional perspective in their patient management. Competency is tested here

Project timeline
Education of Municipality-based Physiotherapists in Managing Disabling Low Back Pain
- An Observational Study

*=Live patient demonstrations by supervisor. All supervisors trained in Cognitive Functional Therapy according to <https://doi.org/10.1093/pn/pnaa034> and <https://doi.org/10.1080/09593985.2022.2151333>

#= Clinical supervision session, 3 cases a day. Participants assess and design intervention under supervision in groups of 4-5 + one supervisor

Figure 1 A schematic overview of the project timeline

Statistics

Statistical analysis will be performed using the appropriate statistical method according to the specific aims investigated. All demographic variables will be presented as means (\pm standard deviations), median [Interquartile range], or ratio (%) depending on type and distribution of data. All primary and secondary outcomes will be analysed using paired tests (parametric or non-parametric based on normality), comparing baseline data and data 3 months after study start.

The sample size calculation is based on the previous findings of Ussing et al (2020)¹ which included a similar population and was conducted in a specialist spine clinic in a secondary setting. Based on these findings, we expect to find a 30% group difference in disability in favor of the post-education group. With a mean of 36 (SD 18) pre-intervention and 28 (SD 18) post-intervention, we expect that N=100 participants in each group will be sufficient to achieve an alpha level of 0.05 with a 0.8 power assuming a 10-15% dropout-out rate.

Ethical considerations

Participation in the study does not imply any risks for the patients. All study related procedures are either clinically indicated or do not come with any risk or harm. The patient needs to spend a little extra time filling out project-specific questionnaires as compared with standard care. The overall burden of participating is outweighed by the potential gain. This study is conducted in full conformance with the principles of the Helsinki Declaration. However, the project falls outside the scope of the ethical committee (regional and national) in Denmark as it falls under quality assurance.

¹ <https://pubmed.ncbi.nlm.nih.gov/32221554/>

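### Örebro is both an entry threshold and a secondary outcome tested against baseline; if the eligibility score serves as that baseline, regression to the mean alone can produce an apparent improvement

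*Combined protocol and SAP*

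**What the plan says.** - **Entry.** The Inclusion Criteria ask for "A score over 40 on the Örebro Musculoskeletal Pain Questionnaire". This is a one-sided cut. No upper limit, scale range or questionnaire version is given.
- **Outcome.** The Secondary outcomes list includes "Örebro Musculoskeletal Pain Questionnaire 3 months after entering the study".
- **Analysis.** The Statistics section states: "All primary and secondary outcomes will be analysed using paired tests (parametric or non-parametric based on normality), comparing baseline data and data 3 months". No other outcome test is named. The sample-size paragraph assumes a difference between the pre- and post-education groups, but the analysis text gives no test for it.
- **Timing.** In the Schedule of procedures and assessments, step 1, the physiotherapists "will recruit eligible patients (N=4 each, total N=100") and these patients complete "project-specific questionnaires (see *procedures*) at the start and at the end of the rehabilitation program". Step 3 adds the second cohort: "Point 1 is repeated on an additional 100 patients who undergo rehabilitation after the physiotherapists have completed the course".
- **Not stated.** The protocol does not say when or on which form the eligibility score is obtained, or whether it is distinct from the baseline score. The list headed 3 month follow-up omits Örebro, although the Secondary outcomes list places it at 3 months.

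**The concern.** When patients are admitted because a measured score lies above a threshold, the admitted group contains people whose score was temporarily high. Someone whose usual score is at or below 40 gets in only on a high reading, and someone usually a little above 40 is left out on a low one. The admitted group's average reading therefore overstates its usual level, and a second reading tends to be lower even if nothing has changed.

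A paired test "comparing baseline data and data 3 months after study start" has no reference group, so it cannot tell this fall from a real improvement. Of the listed outcomes, only Örebro is also an entry threshold. A significant fall in the post-education cohort could be taken as support for the education programme when part or all of it comes from selection.

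**Working it through.** **Plan's own figure.** There is none for Örebro. The sample-size inputs ("With a mean of 36 (SD 18) pre-intervention and 28 (SD 18) post-intervention") concern disability and cannot stand in for an Örebro mean or SD. The only planned number used here is the cohort size: 100 patients with the upper dropout figure of 15% gives 100 × 0.85 = 85 completers, or 2 × 85 = 170 if both cohorts are pooled.

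**Assumptions.** Scores are bivariate normal with equal mean and SD at both times, and there is no true change. The eligibility score is the baseline. The retest correlation ρ over 3 months runs from 0.9 to 0.5. The test is a paired t-test at two-sided 5% (the plan does not state sidedness), counting only significant improvements, so the nominal rate is 2.5%.

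**Formula.** With cut-off c and a = (c − mean)/SD, the expected fall from selection alone is

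(1 − ρ) × SD × φ(a) / (1 − Φ(a)).

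It is positive whenever ρ is below 1. The share of referrals removed by the cut is Φ(a).

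**Example in points.** Assume mean 50 and SD 15. Then a = (40 − 50)/15 = −0.667 and φ(a)/(1 − Φ(a)) = 0.427. For ρ = 0.6 the fall is 0.4 × 15 × 0.427 = 2.56 points. For ρ = 0.8 it is 0.2 × 15 × 0.427 = 1.28 points.

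**Range without assuming a mean or SD.** The table is indexed by the share of referrals that the cut removes. The fall comes from the formula and the rates from 4,000 simulated studies per cell. Each range runs from ρ = 0.9 to ρ = 0.5.

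| Cut removes | a | Apparent fall (SD of unselected scores) | False improvement, 85 completers | False improvement, 170 pooled |
|---|---|---|---|---|
| 2% | −2 | 0.006-0.028 | 3.0-4.6% | 3.8-5.4% |
| 16% | −1 | 0.029-0.144 | 8.5-27% | 14-50% |
| 31% | −0.5 | 0.051-0.255 | 19-69% | 31-94% |
| 50% | 0 | 0.080-0.399 | 38-98% | 65-100% |

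The non-parametric alternative allowed by the plan was not simulated, but it is also a one-sample test of change and has no reference group either.

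**Do the remedies work?**
- *Separate baseline.* With selection on a screening score, a later score as baseline, reliability 0.8 and independent errors, the false-improvement rate was 2.4% whether the cut removed 16% or 50%. That is nominal.
- *Between-cohort comparison.* Comparing change between two cohorts of 85 selected by the same cut gave two-sided error of 4.5-5.7% against a nominal 5%. Adjusting the 3-month score for baseline follows the same logic: with the same cut and the same referral population, the expected 3-month score given baseline is the same in both cohorts when there is no effect.

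**The case against.** **The premise is not in the text.** The full effect needs the eligibility score to be the baseline. Step 1 of the schedule suggests otherwise: patients who are already eligible are recruited and then complete questionnaires at the start of rehabilitation. If Örebro is on that form and that score is the baseline, the mechanism largely disappears. This objection stands in part. The text leans that way but never says that the two scores are distinct, and the project timeline figure is not available to settle it. The 2.4% result also assumes independent errors; two readings taken close together may share the same temporary elevation.

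**The size is assumed.** This stands. Patients with disabling back pain referred from a spine centre may nearly all score well above 40, and the effect is then negligible (first row of the table).

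**The consequence is limited.** Within-cohort change already mixes natural course and usual rehabilitation, so it could not isolate an education effect even without selection. The comparison that answers the objective is between cohorts, where the shared cut cancels. This is correct, but that comparison is not in the analysis text, and the paired test that is there remains exposed.

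**A stronger reading to avoid.** A reader might infer that Örebro will show improvement in both cohorts whatever happens. The documents do not support this, because neither the baseline rule nor the score distribution is given. Nor do they support extending the point to the primary outcome: there is no entry threshold on Roland Morris, and any indirect carry-over through correlation between the scales is not quantified here.

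**Conclusion.** The point holds conditionally. The plan selects on Örebro, tests Örebro by paired change, and does not protect the baseline from the selection. If one score serves both purposes, regression to the mean can produce a significant improvement with no true change. The probability for one cohort of 85 lies anywhere from close to the nominal 2.5% to near certainty, depending on how many referrals the cut excludes and on the retest correlation; the documents fix neither. If the baseline is a separate, later score with independent errors, the problem essentially vanishes. The finding is therefore an unprotected analysis of one secondary outcome, not a demonstrated bias.

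**What to change.** The cut itself need not change. In the Statistics section:

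1. Test Örebro as the pre- versus post-education difference at 3 months, adjusted for baseline Örebro. The same cut applies to both cohorts, and this contrast matches the objective and the sample-size premise.
2. Report the within-cohort Örebro change descriptively, without a p-value or a claim of improvement.
3. State that baseline Örebro is the score in the start-of-rehabilitation questionnaire, completed after eligibility is settled, and not the eligibility score.

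Also reconcile the 3 month follow-up list with the Secondary outcomes list, so that it is clear that Örebro is collected at 3 months.

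**Cost.** A few sentences. A within-cohort significance claim for Örebro is given up, and patients may complete the questionnaire twice before treatment. The between-cohort contrast removes the selection effect common to both cohorts. It does not remove other differences between two cohorts recruited one after the other, and it relies on the referral population and the use of the cut staying the same.

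### Exclusions that call for judgement have no named assessor and no fixed definition, so if the trained physiotherapists apply them, eligibility could differ before and after the course

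*Combined protocol and SAP*

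**What the plan says.** Under Participants, the protocol states "Eligibility is determined on the following criteria" and does not say who does the determining. Two of the exclusions depend on what an illness does to participation, as well as on the illness being present: "A current diagnosis of psychiatric illness that precludes participation in rehabilitation" and "a neurologic disorder or other disease that may affect the ability to participate in a municipality-based rehabilitation program". Neither comes with a threshold or a list of conditions. A third, on stenosis and radicular pain, depends in part on whether the findings match the clinical picture.

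The first inclusion criterion is the same for both cohorts: "Referred to municipality rehabilitation from the Spine Centre of Southern Denmark".

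The Schedule of procedures and assessments, point 1, says "All participating physiotherapists (N=25) will recruit eligible patients", four each. Point 2 says "The participating physiotherapists will undergo a 13-day educational intervention". Point 3 repeats point 1 on 100 further patients once the course is complete.

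Module 1 covers differential diagnostics, co-morbidity among the factors contributing to pain, and "management of patients with dominant cognitive and emotional factors". The Intervention section also says the project will look at whether the physiotherapists' assessment priorities change after the course.

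The Statistics section specifies paired tests of baseline against 3 months. The sample size paragraph, by contrast, rests on a difference between the pre- and post-education groups.

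**The concern.** Comparing two cohorts recruited at different times requires that the entry criteria mean the same thing in both. Age, language, the Örebro threshold and recent stabilizing surgery are fixed facts. Whether an illness rules out or affects participation is not: two clinicians can disagree, and one clinician can change view. The course covers skills that bear on that view.

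The effect could run either way. Physiotherapists more confident with complex patients might admit some they would have excluded before, which would tend to hide a benefit. Sharper differential diagnosis might exclude some they would have admitted, which would tend to create an apparent one.

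This is separate from the choice of whom to invite among eligible patients. Inviting every eligible patient in both phases would not help if the meaning of eligible had moved. The plan describes no log of exclusions, so a shift could go unseen, and no adjustment between cohorts.

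**Working it through.** **Step 1. What the text establishes.**

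| Link in the argument | Status |
|---|---|
| Two exclusions need judgement, a third in part | Stated in Exclusion Criteria |
| The same physiotherapists recruit before and after the course | Stated in Schedule, points 1 to 3 |
| The course covers related skills | Stated in Module 1 |
| The physiotherapists apply the exclusions | Not stated; the assessor is unnamed |
| The criteria are held constant across phases | No step described |

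The concern is therefore conditional on the fourth line.

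**Step 2. The plan's sample size.** Inputs from Statistics: means 36 and 28 (difference 8), SD 18, alpha 0.05 (taken as two-sided), power 0.80, drop-out 10-15%.

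- n per group = 2 × (1.96 + 0.8416)² × 18² / 8² = 79.5, so 80.
- With drop-out: 80/0.90 = 88.9, so 89; 80/0.85 = 94.1, so 95.

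The planned 100 per group is sufficient, as the plan says. With 15% drop-out, 85 per group remain and power is 82.6%.

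**Step 3. What a shift in eligibility could do (illustration only).** The documents give no rate at which decisions might change. Assume a share f of one cohort differs because of changed application of the criteria, and that these patients differ by D points from the rest. The cohort mean moves by f × D. Take f from 5% to 20%, and D from 9 to 18 points (0.5 to 1 SD).

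| f | D | Shift | Share of the 8-point difference |
|---|---|---|---|
| 5% | 9 | 0.45 | 5.6% |
| 10% | 18 | 1.8 | 22.5% |
| 20% | 18 | 3.6 | 45% |

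**Step 4. Effect on an unadjusted comparison of 3-month scores between cohorts.** With 85 per cohort, the standard error is 18 × √(2/85) = 2.76.

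- No true effect, shift 1.8: 1.8/2.76 = 0.65 standard errors; a two-sided 5% test rejects about 10% of the time.
- No true effect, shift 3.6: 3.6/2.76 = 1.30 standard errors; it rejects about 25% of the time.
- True effect 8 with an opposing shift of 2: net difference 6; power falls from 82.6% to 58.4%.

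**Step 5. Which analyses these figures do not describe.** The paired tests compare each patient with himself or herself, so a different baseline level alone does not bias them. If the affected patients differ by the same D at baseline and at 3 months, a comparison of change scores between cohorts also removes the shift. What remains is any difference in how much such patients improve, and nothing in the documents allows that to be sized.

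**The case against.** The strongest reply is that the central premise is not in the text. Recruiting eligible patients does not mean deciding who is eligible. A reader might infer that the physiotherapists do apply the exclusions and that the course therefore changes the study population; the documents support only that this can happen, since no assessor is named. That limit stands, although the silence is itself what needs correcting.

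Second, the Spine Centre has already judged every patient suitable to refer to rehabilitation, in both phases. Few of them are likely to have an illness that rules it out. This also stands: the pool of decisions that could change may be small, and the 5-20% range is assumed.

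Third, the psychiatric criterion requires a current diagnosis, which is a matter of record; only its consequence for participation is judged. Nor does the text equate the cognitive and emotional factors taught in Module 1 with diagnosed psychiatric illness. Both are fair, and they weaken the link without removing it. The second criterion reaches any other disease and is much more open.

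Fourth, a reader might infer that adjustment is impossible because the listed demographic items contain no clear co-morbidity or mental-health item. That goes too far. Patients complete the project questionnaires at the start of rehabilitation, and the Statistics section relies on baseline outcome data, so baseline scores are available for adjustment.

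Fifth, a reader might take 10% and 25% as false-positive rates for this study. They are not: the Statistics section specifies paired tests and names no test between cohorts.

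**Conclusion.** The point holds in conditional form. The plan leaves judgement-based exclusions undefined and unassigned, and the only recruiters it names are the people whose assessment it expects might change between cohorts. If they apply the criteria, the pre- versus post-education comparison can be confounded. That matters because the objective concerns change in patient outcomes following the education and the sample size rests on that comparison.

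Size and direction cannot be determined from the documents. Under the stated assumptions the shift is 0.45 to 3.6 points on the scale of the sample size paragraph, or about 6% to 45% of the planned difference; the Spine Centre's prior referral makes the lower end more plausible. The change is worth making because it costs little, and because exclusion decisions not recorded in the first phase would be hard to reconstruct later.

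**What to change.** Before the first cohort is recruited:

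1. Write one fixed definition of the two participation-based exclusions, and of the judged part of the radicular pain exclusion, that can be read from the existing referral record.
2. State who applies it. Apply it identically in both phases, before the physiotherapist's own assessment, and allow no study exclusion on these criteria outside it. This does not require Spine Centre staff to screen.
3. Log exclusions, and report them by reason and phase.
4. Compare baseline disability, pain and Örebro scores between cohorts, and adjust the between-cohort comparison for them.

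The cost is protocol wording, a short log and two sentences in the Statistics section. The documents do not describe what the referral record contains, so check that the definition can be read from it. A record-based rule may enrol a few patients who cannot complete rehabilitation, adding slightly to drop-out in both cohorts; 100 per group leaves a little room (95 needed at 15% drop-out). Adjustment for baseline scores will not remove differences in prognosis that those scores do not capture, so the fixed definition matters most. Decisions about care are unaffected.

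### The primary RMDQ is defined and analysed at 3 months after entry, but the schedule collects questionnaires at the start and end of rehabilitation, and no readable text reconciles the two

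*Combined protocol and SAP*

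**What the plan says.** The Primary Outcome section gives "Roland Morris Disability Questionnaire 3 months after entering the study". The secondary outcomes (pain intensity, Örebro, work ability, satisfaction) carry the same 3-month timing. The Statistics section says that all primary and secondary outcomes will be analysed with paired tests, "comparing baseline data and data 3 months after study start".

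The section Schedule of procedures and assessments sets a different rule. In point 1, the patients recruited before the education complete the questionnaires "at the start and at the end of the rehabilitation program". Point 3 carries this over to the second cohort: "Point 1 is repeated on an additional 100 patients who undergo rehabilitation after the physiotherapists have completed the course".

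The 3 month follow-up list adds "Roland Morris Disability Questionnaire at 3 months after discharge", without saying whether this is a primary, secondary or other measurement.

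No section gives the length of the rehabilitation programme. The Intervention section says that "individual needs and goals are embedded into the rehabilitation", and also: "The project will investigate whether priorities within assessment and choice of management change after the educational intervention".

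**The concern.** One rule is tied to time since entry and the other to discharge. Staff working from the numbered steps would collect the form when rehabilitation ends, while the outcome definition and the analysis call for a form at a fixed 3 months. Two things are at stake.

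- **The paired tests.** They are specified for baseline against 3 months. A form timed by discharge supplies a score from another time, and that time may vary from patient to patient.
- **The comparison of cohorts.** The sample size rests on a difference between patients treated before and after the education. The project asks whether choice of management changes after the course. It is an inference, not a statement in the documents, that such a change could alter programme length. If it did, the two cohorts would be measured at different times since entry, and any effect of the education could not be separated from elapsed time.

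**Working it through.** **The time points side by side**

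Let L be programme length in months, with entry at the start of rehabilitation and discharge at its end. Both are natural readings, but neither is stated.

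| Source | When the RMDQ is taken | Months from entry |
|---|---|---|
| Primary Outcome | fixed time after entry | 3 |
| Statistics | fixed time after study start, read as each patient's entry | 3 |
| Schedule, points 1 and 3 | end of rehabilitation | L |
| 3 month follow-up list | fixed time after discharge | L + 3 |

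**Can the rows be made to agree?**

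1. The schedule agrees with the definition only if L = 3. The offset is otherwise L − 3 months. The documents give no value for L.
2. The after-discharge measurement cannot stand in for the primary, because L + 3 = 3 only if L = 0. Its list also differs in content: Örebro appears only among the after-entry outcomes and PATH only in the after-discharge list. It is probably an additional follow-up, but its status should be stated.
3. Point 1 refers the reader to the procedures for the questionnaires. That section leads back to outcomes timed at 3 months after entry, so the reference restates the mismatch.
4. A common length of 3 months cannot be assumed, since the programme is described as built around the individual patient and no duration is set.

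**How many patients**

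- Per cohort: 25 physiotherapists × 4 patients = 100, which is the plan's own figure.
- Both cohorts: 100 + 100 = 200.
- After the plan's assumed 10–15% dropout: 200 × 0.90 = 180 to 200 × 0.85 = 170 follow-up measurements.

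**Form of the possible bias**

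Assume, for illustration, that the RMDQ changes by s points per month around this time, equally in both cohorts.

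- Error in a cohort's mean change from baseline: about s × (mean L − 3).
- Error in the difference between cohorts: s × (mean L post − 3) − s × (mean L pre − 3) = s × (mean L post − mean L pre).

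The second error is zero if the mean lengths are equal. The first is not, unless mean L happens to be 3. Neither s nor L is in the documents, so no value can be put on either. The sample-size calculation plays no part in this point.

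**The case against.** The strongest objection is that the schedule heading points to Figure 1, the project timeline, which is the likeliest place for the forms to be set against time since entry and which could not be seen. Harmless readings also exist. Point 1 may be shorthand for a programme of about 3 months, or it may describe an extra form at the end of rehabilitation. The 3-month timing is explicit for the primary and every secondary outcome, so the schedule is the outlier. The Intervention section speaks of content and choice of management, never of duration. The harm needs three things at once: forms collected at discharge, mean lengths that differ between cohorts, and RMDQ scores still changing over that gap. Finally, the tests named are paired, so a bias between cohorts does not bear on them directly.

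Much of this limits the claim without removing it. The figure might reconcile the timing, so the point is confined to the readable text; even a clear figure would leave the wording of points 1 and 3 at odds with the definition. Neither harmless reading is supported by anything written. The between-cohort bias is conditional and is put no higher than that. The remark about paired tests cuts the other way as well, because a form timed by discharge gives those tests the wrong time point whether or not programme length differs between cohorts.

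**Conclusion.** The concern holds. On the readable text, following the schedule collects the primary outcome at a different time from the one defined and analysed, except for patients whose programme happens to last 3 months. This is a contradiction between sections, not merely missing detail, and it reaches the primary measurement of all 200 planned patients.

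The offset is L − 3 months, with L unknown. Bias between cohorts would arise only if mean programme length differed between them while RMDQ scores were still changing; its size cannot be computed from the documents. The conclusion rests on reading study start in the Statistics section as each patient's own entry, and on Figure 1 not having been available. The mismatch in wording is certain; the practical harm depends on how long programmes last and which rule staff follow. It should be fixed.

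**What to change.** - Amend schedule points 1 and 3 so that every patient in both cohorts receives the primary and secondary questionnaires, including Örebro, at 3 months from their own baseline questionnaire, with a stated window and regardless of discharge date. This follows the plan's own outcome definition.
- In the Statistics section, replace study start with each patient's entry.
- Label any RMDQ taken at the end of rehabilitation or after discharge as secondary.
- Check that Figure 1 shows the same time points.

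The cost is wording, plus one extra questionnaire per patient (1 × 200 = up to 200 in total) if the end-of-rehabilitation form is kept. Digital delivery is one option: access to E-boks is already an inclusion criterion, although the plan does not say that questionnaires are sent that way. The drawback is that patients still in rehabilitation at 3 months are measured mid-programme, so their status at the end appears only in a secondary form. If the sponsor knows that all programmes last 3 months, saying so would remove the contradiction, but a fixed time from entry also protects the comparison if lengths vary.
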